5.1.3 Handling Missing Data

Baseline Values

If values are missing at the baseline visit (Day 0/1), and the data are also recorded at screening, then the screening value will be used in the summaries and calculations of change from baseline. Otherwise, the baseline value will be missing for safety and efficacy endpoints.

Missing Efficacy Assessments

The missing data methods are an integral part of the data analysis for efficacy and are described in full in [Section 5.3](#). For the primary analyses of mICARS, the use of a mixed-effect model repeated measure (MMRM) model allows for missing data and assumes the data are missing completely at random (MCAR), so no imputations will be performed.

For sensitivity analysis, several multiple imputation methods will be used:

1. Impute all missing data within the original treatment group.
2. Impute all data missing due to COVID-19 related restrictions to the original treatment group and impute from the control group (Jump to Reference) for all other missing data. The COVID-19 disruption is across the entire study and can be considered as random across subject characteristics and factors that may be related to treatment or outcome, so imputation assuming Missing at Random should be appropriate. Additional factors, such as the number of treatments received, can be added to the imputation model. Details to show that these subjects continued their visits up to the point of restrictions being imposed by the pandemic and did not discontinue treatment due factors related to the study protocol or outcome will be provided.
3. Impute all missing data from the control group (Jump to Reference).

In addition, last observation carried forward [LOCF] and observed cases [OC] will be used. The LOCF method will employ the last observation carried forward; this may be the baseline value if the subject has no follow-up values. The OC method will employ only observed cases for the time points of interest (i.e., for repeated measures analysis of Visit 6 [“Month 3”] and Visit 9 [“Month 6”] both mICARS must be observed/collected to be included in the analysis). A specific analysis using retrieved dropouts will not be performed (see [Section 5.10](#)).

Missing data for all other efficacy analyses not using MMRM will use Multiple Imputation #1 as described above), with the other imputation methods, LOCF and OC, for sensitivity.

Missing Values When Computing Instrument Scores

In the computation of scores for the instruments in use (for example, ICARS), missing values will be handled according to published guidelines/instructions related to the instrument.

In the case of ICARS, the published guideline/instructions will take precedence, but the following rules will be applied if not addressed in the published guideline/instructions.

- If an individual item is missing from the Day 1 ICARS, it will be taken from the Day 0 ICARS.
- If an individual item is missing from a follow-up visit assessment, the same item will be used from the local rater ICARS data.

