To maximize the consistency of the data obtained from the ICARS, the same neurologist, qualified, trained, and certified in the use of the ICARS and with expertise in the field of AT disorders, will evaluate the same patient at approximately the same time throughout the study. ICARS ratings should be completed without consulting scores from the previous visit. In addition, each ICARS administration will be video recorded according to a standardized procedure. The video recordings from each patient will be sent to central remote raters, where they will be blindly evaluated in random order. The ICARS ratings from the central remote raters will be used for the primary efficacy endpoint analysis.

The ICARS will be performed at screening and repeated twice at Baseline, on Day 0 and on Day 1 prior to administration of study medication. Both the Day 0 and Day 1 assessments will be videotaped and scored by the local rater. The Day 1 assessment video will be rated by the central rater and used as a baseline covariate in the analysis. In the event that the Day 1 assessment could not be performed, or is not available, the Day 0 assessment will be rated by the central rater and will be used as the baseline.

12.2 **Clinical Global Impression (CGI-C and CGI-S)**

The CGI (Guy, 1976) is the general name for two scales, the CGI - Change scale (CGI-C) and CGI- Severity scale (CGI-S). The CGI-C scale assesses the change in the patient's clinical status from **baseline** using a 7-point scale, ranging from 1 (very much improved) to 7 (very much worse), with a score of 4 indicating no change. In the current study, the change from the patient's baseline condition will be assessed at all post-baseline visits, and the mean rating of change at Endpoint (Month 6 or early discontinuation) will be the key secondary efficacy measure. The rater performing the CGI-C will be different from the rater performing the ICARS rating, and will assess the patient without access to the ICARS ratings or safety data. A guideline for performing the rating of change using the CGI-C is provided below.

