To maximize the consistency of the data obtained from the ICARS, the same neurologist, well trained in the use of the ICARS and with expertise in the field of AT disorders, will evaluate the same subject at approximately the same time throughout the study. At each site, qualified raters will be trained to criteria at the Investigator's meeting and will receive ongoing training during the trial. The ICARS rater will perform the rating on each subject without consulting the results from the previous visit. In addition, video recording will be performed during each ICARS administration (though not required at Screening), according to a standardized procedure. The video recordings from each subject will be sent to an independent remote rater, where they will be blindly evaluated in random order. The speech domain items (Items 15 and 16) will be rated only by local raters who are familiar with the local language. The ICARS ratings from the independent remote rater, making use of the speech domain items which come only from the local raters, will be used for the primary efficacy endpoint analysis which is the mICARS.

Rating of the ICARS will be performed 24 hr before Baseline (Day -1) and at Baseline (Day 0); the Day 0 assessment will be recorded and used for determining changes from baseline on treatment. The ICARS will also be assessed at Visit 6 ("Month 3") and at Endpoint (Visit 9 ["Month 6"] or at early discontinuation) during the Initial Treatment Period, and at Visit 12 ("Month 9") and Visit 15 ("Month 12") (or at early discontinuation) during the Extension Treatment Period.

The ICARS score is the total sum of the sub scores and ranges from 0 to 100, with 100 being indicative of the most severely affected outcome. The 'Modified' ICARS (mICARS) score is the total sum of the sub scores excluding Items 17-19 related to oculomotor function and Items 8-12 related to kinetic function; these sub scores have been removed per **CC** request. The 'Modified' ICARS score ranges from 0 to 54, with higher scores indicative of more severely affected outcome.

The baseline score by the central rater for the ICARS will be assessed at Visit 1, and the score closest to dosing will be accepted; therefore, the Day 1 value will be used where present, otherwise the Day 0 value will be used. If both the Day 1 and Day 0 assessments are missing, the Screening value by the local rater will be used.

Initial 6-Month Treatment Period

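### Two SAP fallbacks mix local and central raters within a patient's primary mICARS change; the likely bias is small, and SAP wording plus one sensitivity table would settle it

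*SAP*

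**What the plan says.** Protocol 12.1.3 names the source of the primary endpoint: "The ICARS ratings from the central remote raters will be used for the primary efficacy endpoint analysis". Protocol 7.3 adds that these raters are blind to treatment, see the videos in random order and are not told the visit. For baseline, protocol 12.1.3 says "Both the Day 0 and Day 1 assessments will be videotaped and scored by the local rater". The central reader takes Day 1. Only if Day 1 was not done or is unavailable does the protocol say that "the Day 0 assessment will be rated by the central rater and will be used as the baseline". It has no further fallback.

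The SAP adds three uses of local scores:

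- **Speech (SAP 4):** "The speech domain items (Items 15 and 16) will be rated only by local raters who are familiar with the local language".
- **Missing baseline (SAP 4),** directly after the rule for the central rater's baseline score: "If both the Day 1 and Day 0 assessments are missing, the Screening value by the local rater will be used".
- **Missing items (SAP 5.1.3):** at baseline, "If an individual item is missing from the Day 1 ICARS, it will be taken from the Day 0 ICARS", with no rater named; at follow-up, "If an individual item is missing from a follow-up visit assessment, the same item will be used from the local rater ICARS data". For both item rules, "the published guideline/instructions will take precedence".

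SAP 5.10, which lists changes from the protocol, mentions none of these. The follow-up item rule sets no limit on the number of items and asks for no flag or count by arm.

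**The concern.** A change score is clean when the same kind of rater stands on both sides, because a constant difference in scoring habit then cancels. The follow-up item rule and the Screening fallback each replace one side only, so the local-central difference stays in the change. The follow-up rule also lets in a score made at the site visit by the neurologist who examines the same patient throughout. That rater cannot be masked to visit or order in the way a video reader can. That the local rater knows the visit is an inference from this arrangement, not a statement in the documents.

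The Screening fallback has a second weakness. Protocol 12.1.3 says that local Day 1 and Day 0 scores are collected. They lie closer to dosing, which is the criterion SAP 4 itself uses to choose a baseline, yet the rule passes over them. A baseline taken from the wrong source also enters the MMRM twice, in the change and as the covariate.

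At stake is whether a reader can tell how far the primary result depends on masked central readings.

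**Working it through.** **Step 1. Which rater stands on each side.**

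| Situation | Baseline | Follow-up | Offset left in the change |
|---|---|---|---|
| Nothing missing, non-speech items | central | central | none |
| Speech, Items 15-16 | local | local | none |
| Item missing centrally at follow-up | normally central | local | + offset |
| Day 1 and Day 0 missing | local Screening | central | − offset |

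The offset is local minus central. The two fallbacks act in opposite directions. The baseline item is only normally central because the Day 0 item rule names no rater, and a central Day 0 reading is planned only when Day 1 is unavailable.

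**Step 2. How much of the scale is central.** mICARS runs from 0 to 54 (SAP 4). Posture and gait give 34 points and speech 8, so the retained kinetic items give 54 − 34 − 8 = 12. The centrally rated part is 54 − 8 = 46 points.

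**Step 3. Bias in the treatment contrast.** Let p be the share of patients in an arm with a substituted score and d the mean offset per affected patient. Bias = p(high)·d(high) − p(placebo)·d(placebo). With the same d in both arms this is [p(high) − p(placebo)] × d. The documents give neither p nor d, so both are assumed over a range:

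| Difference in share | d = 0.5 | d = 1 | d = 2 | d = 3 |
|---|---|---|---|---|
| 0 | 0 | 0 | 0 | 0 |
| 5 points | 0.03 | 0.05 | 0.10 | 0.15 |
| 10 points | 0.05 | 0.10 | 0.20 | 0.30 |
| 20 points | 0.10 | 0.20 | 0.40 | 0.60 |

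The planned difference is 3.0 to 3.7 (SAP 5.1.7). The worst cell is 0.60/3.0 = 20% of the lower figure.

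**Step 4. Added noise when the arms are balanced.** The plan's figure comes first: 54 per group, difference 3.0, SD 7.0, two-sided 0.05, two repeated measures, stated power 88.3%. Taking the mean of two uncorrelated measures, the SD is 7.0/√2 = 4.95, the standard error is 4.95 × √(2/54) = 0.953, and 3.0/0.953 − 1.96 = 1.19, which gives 88.3%. The whole power table reproduces this way. The zero correlation is not stated in the plan; it is used here only to show the change in power.

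Now let a share f of patients carry a rater difference with SD s. The SD becomes √(7.0² + f·s²). With f = 0.20 and s = 3, the top of the assumed ranges (f 5-20%, s 1-3 points), this is √(49 + 1.8) = 7.13, and power is 87.1%.

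**The case against.** The strongest reply is that these rules may seldom operate and should do little when they do. The item rule covers individual items and yields to a published guideline that is not in the documents, so it may rarely apply. On a plain reading of the Screening rule, Day 1 and Day 0 assessments that are missing did not take place at all, and then there is no local score to pass over. Baseline ratings are made before dosing, and assignment happens on Day 1 just before dosing (protocol 9.3), so a missing baseline should be unrelated to arm and add noise rather than bias. Site raters are blind to treatment (protocol 10.4), have no access to other scales or safety data (11.2, 12.5), do not see cortisol or ACTH results (11.6, 13.5) and should not consult previous scores (12.1.3). SAP 6.3.2 also plans separate tables for the Posture and Gait domain, 34 of the 46 central points, with no speech items in it.

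Most of this stands, and it limits the point. Three things remain. The Screening sentence follows a rule about the central rater's score, so it can be applied when the central reading is missing but the local one exists; the wording does not exclude that. The domain tables remove speech but not the substitutions. And no planned analysis uses central items alone.

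**Conclusion.** The point holds as a gap in rater consistency and disclosure. Both fallbacks depart from protocol 12.1.3, and neither is declared. On the assumed ranges the bias in the contrast is about 0 to 0.6 points, and it is zero if substitution rates and offsets are equal across arms. Nothing in the documents indicates an imbalance. The noise costs about one percentage point of power at most (88.3% to 87.1%). These sizes rest on assumed frequencies and offsets.

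A reader might infer more, and the documents do not support it:

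- **That treatment masking is broken.** The site rater's safeguards cover treatment and safety data; only visit and order masking is lost.
- **That the speech items are part of the mismatch.** They are local at baseline and at every follow-up, for a stated language reason. Only their absence from SAP 5.10 is at issue.
- **That local scores enter on one side of the trial's change scores only.** Each rule alters one side, but the two act in opposite directions.
- **That the Screening score is inflated or deflated to secure eligibility.** Inclusion criterion 2 does use the local Item 1 score, but favourable scoring is conjecture, and it would precede treatment in every arm.
- **That an error of several points in one patient threatens a difference of 3.0 to 3.7.** That compares an individual error with a group mean; only the difference between arms counts.

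**What to change.** Amend the SAP before unblinding:

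(a) **5.1.3, item missing centrally at follow-up.** Set it to the central baseline item plus the local change in that item (local follow-up minus local Day 1, else local Day 0). A constant offset then cancels, and the central baseline remains the single MMRM covariate.

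(b) **4, no central baseline.** Use local Day 1, then local Day 0, and local Screening only if neither exists. Keep the central follow-up scores. Some mismatch remains for these patients, but replacing masked follow-up readings with local ones would be a worse trade.

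(c) **5.3.1.** Add one prespecified sensitivity run of the primary MMRM on centrally rated items only, without Items 15-16 and without local substitutions. Report the number of substitutions by arm.

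(d) **5.10.** List the local speech scoring and the substitutions as changes from protocol 12.1.3. In the same edit, name the rater for the Day 0 item rule.

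The cost is SAP wording and one extra table. The protocol already collects the ratings these changes use.

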5.1.4 Handling Data Collected Out of Window

Efficacy scales (e.g., ICARS, QoL, etc.) collected outside of the per-protocol windows (for example, per [Appendix I](#), ICARS is scheduled for collection only at Visit 6, 9, 12, and 15) will be included in the analyses based on the nominal visit label. During the initial 6-month treatment period, Visit 9 (Month 6) must occur within 228 day window for the per protocol analysis. All data will be presented in the listings, in chronological order based on the time of collection.

5.1.5 Handling Data Collected Prior to a Process Event or Interruption

The interruption of an EDS process can result in a repeat EDS process with potentially the repeat of assessments that are scheduled to take place prior to the EDS process at a given visit. If this occurs (a repeat EDS process is conducted and the assessments scheduled to take place prior to an EDS assessment are repeated), the earliest set of assessments that are within the visit window will be used; if both set of assessments are outside of the visit window, then the set of assessments prior to the first EDS process will be used.

5.1.6 Pooling of Investigator Sites

Since the randomization used probabilistic baseline randomization (pBAR) methodology, it was not blocked by site, and the analysis will not be blocked by site.

5.1.7 Determination of Sample Size

Based on the very low prevalence of AT, as well as the high disability, morbidity and mortality, the number of patients available for prospective trials is extremely limited. Furthermore, only aggregate Phase II study results were available ([IEDAT-ERY01-2010 Clinical Study Report](#)). Hence, in the absence of a file with the raw item score for each patient, the treatment effect and variability of the 'Modified' ICARS was unknown. Therefore, the parameters needed to identify an appropriate sample size for this study were estimated using the aggregate Phase II results.

Sample size calculations were based on the analysis of the primary efficacy variable (i.e., 'Modified' ICARS) under the following assumptions.

- For aggregate ICARS, a treatment difference of 3.7 - 4.2 for the high dose versus placebo with respect to ICARS measurements is expected, with a standard deviation of 5.0 - 7.4 ([IEDAT-ERY01-2010 Clinical Study Report](#)).
- For 'Modified' ICARS, the treatment difference is expected to be less than the aggregate ICARS, therefore instead of examining a treatment effect between 3.7 and 4.2, the range between 3.0 and 3.7 was examined. The decrease in treatment effect is expected given that most of the questions in the Kinetic Function domain are not included in the 'Modified' ICARS and [Chessa et al \(2014\)](#) reported this domain as demonstrating the greatest overall improvement.
- For 'Modified' ICARS, the standard deviation is expected to be more than the aggregate ICARS, therefore instead of examining a standard deviation between 5.0 and 7.4, the range

between 5.0 and 8.0 was examined. This increase is expected given that removing questions from health assessment instruments can decrease precision and increase standard deviations (Awad, 2008; McHorney, 1992; McHorney, 1997).

- The primary efficacy variable will be tested, comparing high dose versus placebo at the 0.05 two-sided significance level. Testing of the low dose versus placebo will only proceed if the high dose is significant for the primary endpoint and the secondary endpoint. Consequently, no adjustment for multiplicity is needed for testing the two dose levels.

Table 3 provides power estimates for the range of potential treatment effects and standard deviations. Estimates had to be based on ranges, since point value estimates for 'Modified' ICARS were not available.

Table 3. Power given treatment effect and standard deviation estimates for a sample size of 54

Treatment Effect	Standard Deviation	Power
3.0	5.0	99.3%
	6.0	95.7%
	7.0	88.3%
	8.0	78.7%
3.2	5.0	99.7%
	6.0	97.5%
	7.0	91.9%
	8.0	83.6%
3.4	5.0	99.9%
	6.0	98.6%
	7.0	94.6%
	8.0	87.8%
3.6	5.0	>99.9%
	6.0	99.3%
	7.0	96.6%
	8.0	91.1%
3.7	5.0	>99.9%
	6.0	99.5%
	7.0	97.3%
	8.0	92.5%

[figure not shown]
As seen in the above table, a sample size of 54 provides sufficient power for a study design with two repeated measures to assess the primary efficacy endpoint of change from baseline in ‘Modified’ ICARS between two groups with a two-sided 0.05 significance level, when the treatment effect ranges between 3.0 and 3.7, and the standard deviation ranges between 5.0 and 7.0 (PASS®, Module “Tests for Two Means in a Repeated Measures Design”).

The final sample size was adjusted for 10% loss to follow-up, for a final sample size of about 60 per group. It was anticipated that the screen failure rate would be approximately 25%; therefore, at least 240 subjects would need to be screened to enroll 180 eligible subjects.

Sample size was based on the primary efficacy parameter from the Version 10.0, Final, 16 April 2019 IEDAT-02-2015 protocol, the ‘Modified’ ICARS. The computed sample size is sufficient to maintain at least 80% power for the full ICARS, given the range of treatment differences and range of standard deviations available for the full ICARS from the IEDAT-ERY01-2010 Clinical Study Report described above and the powers computed for the selected ranges of treatment effect and standard deviation for the ‘Modified’ ICARS.

5.1.8 Randomization

The milestones for the randomization process are depicted in Figure 1 and described in Items 1-4 below.

* Randomization (1:1:1; n=180, i.e. 60 per study arm) to ~5-10 or ~14-22 mg EDS or placebo using a minimization procedure for gender and age (< 10 and ≥ 10 years of age) will be done by IVRS

** All remaining placebo patients switch to ~14-22 mg EDS in study IEDAT-03-2018

NOTE: Due to the impact of COVID-19, the company decided to complete enrollment with 175 patients.

Figure 1. Trial periods and randomization/placebo switching time points.

1. **Initial Randomization.** This occurred at the start of the double-blind period. Because this trial enrolled subjects with a rare condition, the sample size was limited. Important balancing factors included gender and age (age < 10, age ≥ 10) and region. There are three treatment groups. For this situation, probabilistic baseline randomization (pBAR), or equivalently, probabilistic covariate baseline minimization was desirable. The placebo switches discussed in Items (2)-(4) were assigned at the time of the initial randomization. (See Figure 2)
2. **Switching of remaining placebo subjects after 6 months of the Initial Double-Blind treatment assignment.** Among subjects initially randomized to placebo who complete their initial 6 months of double-blind dosing, every third such placebo subject was randomized 1:1 to active dose at either the high or low dose level.
3. **Switching of remaining placebo subjects after 9 months of the Initial Double-Blind treatment assignment.** Among subjects initially randomized to placebo who complete their initial 9 months of double-blind dosing, every other such placebo subject was randomized 1:1 to active dose at either the high or low dose level.
4. **Switching of remaining placebo subjects after 12 months of the Initial Double-Blind treatment assignment.** For subjects initially randomized to placebo who complete their initial 12 months of double-blind dosing, all such placebo subjects will have been

randomized 1:1 to active dose at either the high or low dose level. These treatment assignments will be made in the open-label extension study (Study IEDAT-03-2016) for those placebo subjects who continue treatment in that study.

[figure not shown]

Figure 2. Randomization schematic

When the design of the pBAR randomization was in place, simulations were used to test the randomization system. The simulations were designed

1. to subject the pBAR implementation to conditions beyond the control of the study team, such as the order that subjects arrive for randomization, to assess the robustness of the algorithm. The ability of the system to handle re-ordering of the arrival order of subjects was examined to see how well the desired balance was achieved.
2. to examine the extent to which random fluctuation disturbed the balance, both overall, and within the desired strata.
3. to subject the IVRS system implementation to various stresses, as a validation.

